6.5.1 Timeline

Process	B	1	Final	LL. S.
	1	5 \pm 1	8 + 1	15 \pm 2
Eligibility criteria	X			
Informed consent signature	X			
Pregnancy test (if applicable)	X		X	
General and ophthalmological clinical history	X			
Comprehensive ophthalmologic exploration	X	X	X	
Assignment of subject code	X			
Assignment to treatment group	X			
Delivery of medication and start of instillation	X			
Sampling of conjunctival secretion	X		X	
Biomicroscopy	X	X	X	
Global qualification of the researcher		X	X	
Evaluation of concomitant medications	X	X	X	
Delivery of the subject's diary	X			
Evaluation of adverse events		X	X	X
Continuity evaluation		X	X	
Adherence evaluation (per subject's diary)		X	X	
Return of the medication			X	
Returning the subject's journal			X	

6.5.2 Procedures to be performed per visit.

Next, the procedures that will be carried out in each visit are listed, as well as a brief description of these.

6.5.2.1 Basal visit.

- Eligibility criteria: refers to the review by the IP, where it states that the subject can be included in the study by meeting the inclusion criteria and not meeting the exclusion criteria. See 6.2 Eligibility criteria. The IP selects the eye that will be included for the efficacy analysis, indicating it in the clinical note and in the CRF.
- Signature of informed consent: refers to the signing of the written informed consent document. See 10.3 Consent
- Pregnancy test: refers to the performance of a rapid pregnancy test in all women of age who wish to enter the study. By fertile age we understand women who have not had their menopause, defined as 12 months since the last menstrual period in women over 40 years of age, or who have undergone a bilateral hysterectomy or oophorectomy. Women of childbearing age with contraceptive methods including bilateral tubal obstruction should be tested for pregnancy. This test will be performed by the IP or the designated team person according to the instructions of the device delivered by the sponsor.
- General and ophthalmological clinical history: refers to the technical, clinical and legal document in which the patient's health conditions, medical acts and other procedures performed on the patient are recorded chronologically. It includes the anamnesis and comprehensive ophthalmological exploration that allows to discern the patient's eligibility. If the patient is taken from the established consultation of the study center, he / she will be able to use the existing clinical history, only having to perform an update.
- Conjunctival secretion sampling: see section 6.4.3.4 Conjunctival secretion sampling for bacterial culture.
- Comprehensive ophthalmological exploration: it refers to the evaluation of the ophthalmic structures of the subject, eyelids and appendices, ocular surface, anterior segment and posterior segment; not considered within the outcome variables. This evaluation has the purpose of identifying alterations that may interfere with the course of the investigation or identify adverse events. This scan will be recorded in the clinical file, in the CRF only what is considered an adverse event will be reported.
- Assignment of the subject's code: It refers to granting the number that will identify the patient throughout the study. This will be done according to section 6.2.4 Identification of the subject.
- Assignment to the treatment group: It refers to determining the treatment that the patient will follow during the study. It will be done according to section 7. Methods. Assignment of the intervention.
- Delivery of medication: This refers to the delivery of the medication to the patient of the study, by the research center. It will be done according to sections 6.3.1 Managed treatments and 6.3.4.1 Delivery and reception. After each medication delivery, training or re-training of the application of the study medication will be carried out.
- Biomicroscopy: see 6.4.3.1 Biomicroscopy
- Evaluation of concomitant medications: it refers to the interrogation that the IP of the medications that the patient uses, before, during and after the study. They must be registered in the corresponding section in the CRF, including name of active substance,

posology and duration. See: 6.3.3 Treatments and concomitant interventions allowed and prohibited before and during the study.

- Subject's journal delivery: refers to the delivery by the IP, of the subject's daily instrument, to the subject.

6.5.2.2 Visit 1

- Comprehensive ophthalmological exploration: see 6.5.2.1 Baseline visit.
- Biomicroscopy: see 6.4.3.1 Biomicroscopy
- Global qualification of the researcher: see 6.4.3.2 Global qualification of the researcher
- Evaluation of concomitant medications: see 6.5.2.1 Baseline visit.
- Assessment of adverse events: see 6.4.3.3 Evaluation of adverse events
- Continuity evaluation: refers to the determination by the PI and desire of the subject to continue with their participation in the study.
- Evaluation of the adherence: refers to the review of the diary of the subject to evaluate the registration of drug application.
- Global qualification of the researcher: see 6.4.3.2 Global qualification of the researcher

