5.1.2 Clinical picture of acute bacterial conjunctivitis

The symptoms of acute bacterial conjunctivitis can present a wide spectrum of signs and symptoms, and the severity of these. However, classically, the onset of bacterial conjunctivitis with a unilateral foreign body sensation, secretion and conjunctival hyperemia is described. Symptoms can become bilateral in one or two days. The secretion evolves to be more copious and purulent, the "sticky eyes" in the morning are a very common symptom. In some patients the condition is accompanied by pain or burning. Although these symptoms are generally accepted as typical of acute bacterial conjunctivitis, they have not been classified as diagnostic criteria based on evidence for the differentiation between bacterial and viral conjunctivitis. [22]

Conjunctival hyperemia is the rule, being more intense in the peripheral bulbar conjunctiva and less intense towards the limbus. In more severe cases, conjunctival hyperemia can be totally generalized. The secretion can occur throughout the palpebral fissure, or only in the cul-de-sac or as yellowish incrustations on the eyelid margin. [5]

In patients diagnosed with bacterial conjunctivitis, conjunctival hyperemia has been reported in all cases, secretion in 85-90% of cases, foreign body sensation in 90%, and 50% with various degrees of burning or pruritus.[23]

5.1.3 Treatment of acute bacterial conjunctivitis.

Acute bacterial conjunctivitis is a disease with a good prognosis and self-limiting in at least 60% of cases in non-immunocompromised adults. [11] The use of antibacterial therapy is associated with an earlier clinical and bacterial remission, compared with placebo on days 2 and 5 of treatment. These advantages over placebo remain on days 6 and 10, but tend to decrease with time extension. [1]

The choice of antibiotic is usually made empirically. Because a course of 5-7 days with broad spectrum antibiotic is sufficiently effective, you can choose the option that is most convenient; there is still no clinical evidence to suggest the superiority of any particular antibiotic. [1] [24]

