The "Delegation of Responsibilities" and the "Organizational Chart of the Center" must be delivered to the sponsor before the start of the study and updated if the members or their responsibilities are changed.

6.1.2 Documentation to be delivered to the sponsor.

The IP must deliver to the sponsor, before the start of the study:

- Curriculum vitae updated, in Spanish, dated and signed (maximum 10 pages), of the IP and the staff that integrates its organizational chart of the center.
- Copy of IP academic certifications (degree certificate and specialty diploma in ophthalmology, federal professional certificates).
- Copy of academic certifications of the maximum degree obtained, from each one of the members of your research team, that cover their capacity to perform the delegated functions.
- Copy of operating notice or similar issued by corresponding regulatory entity (When applicable)
- Certificate of good clinical practice in force. If the issuing institution does not specify the validity period in the certificate, the date of issue of the certificate must not exceed one year
- Letter of declaration of interests of the IP and subinvestigator.

6.1.3 Closure of the center.

The closing of the center will be carried out once the last visit of the last included subject previously agreed between the sponsor and the IP has been made. The closing process will be according to the internal operating procedures of the sponsor.

It is the sponsor's prerogative to prematurely close a study center, it must inform the IP the reasons for the closure.

6.2 Eligibility criteria.

6.2.1 Inclusion criteria.

- Signed informed consent.
- Age ≥ 1 year.
- Both genders.
- Clinical picture of acute bacterial conjunctivitis defined by:
 - ° Conjunctival secretion
 - ° Conjunctival bulbar hiperemia

6.2.2 Exclusion criteria.

6.2.2.1 General criteria.

- I. Pregnant women, lactating or planning to become pregnant.
- II. Women of reproductive age and who do not have a hormonal contraceptive method, intrauterine device or bilateral tubal obstruction.
- III. Participation in another clinical research study ≤ 30 days before the baseline visit.
- IV. Previous participation in this same study.
- V. That they can not comply with their attendance at appointments or with all the requirements of the protocol.

6.2.2.2 Medical and therapeutic criteria.

- I. Single eye
- II. Presence of corneal abrasion or corneal ulceration in the study eye.

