6.4.3.1 Biomicroscopy

It is the procedure by which, with the use of the slit lamp or biomicroscope, the ocular structures are evaluated thanks to the characteristics of the light source and the optical power of the instrument. A full assessment of the previous segment will be made, which will be recorded in the clinical file.

By means of biomicroscopy **bulbar conjunctival hyperemia, conjunctival secretion will be evaluated and will serve for the evaluation of adverse events and the global qualification.**

Conjunctival hyperemia is defined as the simplest reaction of the conjunctiva to a stimulus, a red appearance secondary to the vasodilation of the conjunctival vessels of variable intensity. He will graduate using the Efron scale. [37] The number will be reported in the CRF, according to the rating granted, in each of the visits. (See Illustration 1)

Illustration 1. Efron scale for conjunctival hyperemia.

The ocular secretion will be classified as 0 = absent, 1 = mild, 2 = moderate and 3 = severe. The number will be reported in the CRF, according to the rating granted in each of the visits.

The clinical remission in the visits will be evaluated as "Yes" or "No", to report "Yes" it must have a grade of "0" in conjunctival hyperemia and "0" in secretion; otherwise, you must report as "No".

6.4.3.2 Global qualification of the investigator.

The global qualification of the investigator constitutes the integral judgment of the clinical picture of the subject, including signs and symptoms, after a routine ophthalmological evaluation and interrogation. It will be classified 0 = cure, 1 = improvement, 2 = no changes compared to before starting treatment, 3 = worsened. It will be registered in the CRF in each of the follow-up visits.

6.4.3.3 Evaluation of adverse events.

The evaluation of adverse events requires a questioning conducted by the IP and the appropriate exploratory techniques for its detection.

The IP will register in the corresponding section of the CRF the EA that the subjects of the study will present.

The management of the EAs will be done according to what is described in section 9.3 Adverse events.

6.4.3.4 Sampling of conjunctival secretion for bacterial culture.

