6.5.2.4 Final Visit

- Pregnancy test: see 6.5.2.1 Baseline visit.
- Conjunctival secretion sampling: see section 6.4.3.4 Conjunctival secretion sampling for bacterial culture
- Ophthalmological examination: see 6.5.2.1 Baseline visit.
- Biomicroscopy: see 6.4.3.1 Biomicroscopy
- Global qualification of the researcher: see 6.4.3.2 Global qualification of the researcher
- Evaluation of concomitant medications: see 6.5.2.1 Baseline visit.
- Assessment of adverse events: see 6.4.3.3 Evaluation of adverse events
- Continuity evaluation: see 6.5.2.2 Visit 1
- Adherence evaluation: see 6.5.2.2 Visit 1
- Global qualification of the researcher: see 6.4.3.2 Global qualification of the researcher
- Return of the medication: refers to the delivery, by the subject, of the excess medication to the research center.
- Return of the subject's diary: refers to the delivery, by the subject, of the tool "subject's diary" to the research center.

6.5.2.5 Security call:

- Assessment of adverse events: see 6.4.3.3 Evaluation of adverse events.

6.5.3 Diagram of the study.

[figure not shown]

Figure 6. Diagram of the study.

6.6 Sample size.

The sample size calculated for the present study is 160 eyes. They plan to recruit 160 subjects, each one will provide an eye for the study, for the analysis of efficacy.

Divided into two intervention groups, each group will be comprised of 80 eyes.

6.6.1 Calculation of the sample size.

The sample size was calculated using the formula for variables of two proportions, likewise the data was entered into the online calculator, software developed in: www.powerandsamplesize.com based on Chow S et al. [39]

Based on the final report of the Phase II clinical study, and the difference found between the intervention of PRO-157, three times a day, against gatifloxacin 0.3%, the calculation of the sample size was made.

The dosage that showed the greatest efficacy was the instillation of 1 drop three times a day. A cure percentage of 88% was observed with the mentioned group. The group that received Gatifloxacin reported a cure rate of 94%. Nevertheless, there was no statistical difference between the groups. [35]

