The sample size was calculated considering the clinical cure rate of 0.88 submitted to the treatment with PRO-157 1 drop three times a day compared to a percentage of 0.94 of the group with Gatifloxacin. It is expected that at least a healing difference of 15% will be present to demonstrate superiority in the upper and lower limits, in order to demonstrate non-inferiority.

The formula for non-inferiority or superiority was used comparing two proportions¹ with a Power (1-β): 90% and an error type 1, α: 5%. Margin or limit, δ: 15%.

$$n = p(1 - p) \left(\frac{Z_{1-\alpha} + Z_{1-\beta}}{p - p_0 - \delta} \right)^2$$

The result is **112 eyes with acute bacterial conjunctivitis**. Considering an increase of 30% (15) due to the probable losses and a balance between the groups, the final **sample size is 160 eyes**.

The intervention will be applied in both eyes, however each subject will only provide one eye for efficacy analysis.

6.7 Recruitment .

The subjects will be recruited from the IP external consultation or referenced from first level centers. Recruitment will be competitive for all centers.

7. Methods Assignment of the intervention.

7.1 Generation of the allocation sequence.

2 strata corresponding to the intervention groups will be used, which will be balanced for each research center. The allocation will be 1: 1. The generation will be done through an electronic system validated by an external provider, previously evaluated and authorized by Sophia Laboratories S.A. of C.V. The information corresponding to this provider will be found in the master folder of the study.

7.2 Blinding mechanism.

Blinding will be performed by the personnel indicated by the Clinical Operations Management of Sophia Laboratories, S.A. of C.V. The vials of both interventions will be re-labeled and the secondary packaging will be masked.

7.3 Implementation.

The sequence will be generated by means of an electronic randomisation system. Said system will be hired by Sophia Laboratories, S.A. of C.V. to a third party. The information corresponding to this third party will be found in the master folder of the study.

7.4 Blinding and masking.

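### No criterion governs the investigator's choice of study eye; if milder eyes are taken in bilateral cases, the trial could lose sensitivity to a real difference between the arms

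*Combined protocol and SAP*

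**What the plan says.** Section 6.5.2.1 (baseline visit, eligibility item) gives the only selection rule: "The IP selects the eye that will be included for the efficacy analysis, indicating it in the clinical note and in the CRF". The protocol contains no worse-eye, first-affected-eye, right-eye or random rule, and no minimum severity.

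The only eligibility condition tied to the study eye is an exclusion in section 6.2.2.2: "Presence of corneal abrasion or corneal ulceration in the study eye". Section 6.2.1 lists conjunctival secretion and bulbar hyperemia as the defining signs but does not say which eye must show them. The summary in section 1 joins the two signs with an *or*.

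Section 5.1.2 says of the disease: "Symptoms can become bilateral in one or two days". Section 6.6.1 says: "The intervention will be applied in both eyes, however each subject will only provide one eye for efficacy analysis". Section 6.4.3.4 has both eyes swabbed.

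The primary outcome (sections 6.4.2.1 and 6.4.3.1) is remission on day 8, which requires grade 0 for both hyperemia and secretion. Section 6.6.1 plans on remission of 0.88 for PRO-157 and 0.94 for gatifloxacin, with a margin of 15 points. Section 5.1.3 describes the disease as "self-limiting in at least 60% of cases in non-immunocompromised adults".

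Safeguards are also stated. In section 6.5.2.1 the eye is chosen at the eligibility step, which is listed before treatment assignment. Section 7.4 blinds the principal investigator and the subject. Section 7.1 balances allocation within each centre.

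**The concern.** When both eyes are affected, the analysed eye depends on site habit. An eye that starts at low grades should reach grade 0 on both signs more easily, and with a planned control rate of 94% there is little room above. If sites tend to take the milder eye, remission would rise toward the ceiling in both arms.

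In a superiority trial, dilution that is equal in both arms works against the sponsor's claim. In a non-inferiority trial with a 15-point margin it works in favour of the test product, because the eyes most likely to show a weaker antibiotic are left out of the analysis. Masking does not prevent this, since the mechanism does not need the investigator to know the treatment. Because the inclusion signs are not tied to the chosen eye, a barely affected eye can also be the analysed eye. None of this can be repaired once eyes have been chosen.

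**Working it through.** **The plan's own figures.** The formula printed in section 6.6.1, with p = 0.88, p0 = 0.94, a margin of 15 points entered as δ = −0.15, one-sided α = 0.05 and power 0.90, gives

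0.88 × 0.12 × [(1.645 + 1.282) / (0.88 − 0.94 + 0.15)]² = 111.6, so 112.

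Then 112 / 0.70 = 160, or 80 eyes per arm; 112 / 2 = 56 per arm if the whole loss allowance is used. Both stated totals reproduce. The formula has the one-sample form. That is a separate matter, and an eye-selection rule does not change the sample size.

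**Inputs for the illustration.** From the documents: control remission 94%, margin 15 points, one-sided 5%, 80 or 56 eyes per arm. Assumed, because the documents give no figures:

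- in worse or only affected eyes the product sits exactly at the margin, 79% versus 94% (failure 21% and 6%);
- a share *b* of 30–70% of patients have two candidate eyes;
- failure in the milder eye is *r* times that in the worse eye in both arms, with *r* = 0.75 or 0.50;
- the milder eye is always chosen.

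**Formula.** Failure in the analysed eyes is multiplied by f = 1 − b(1 − r), so the difference becomes −15 × f points. For b = 0.5 and r = 0.5, f = 0.75: control remission is 1 − 0.06 × 0.75 = 95.5%, test remission is 1 − 0.21 × 0.75 = 84.25%, and the difference is −11.25 points.

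The chance of declaring non-inferiority is found by exact binomial enumeration. Success means that the lower limit of the two-sided 90% Newcombe interval lies above −15 points.

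| Milder-eye failure | Bilateral share | Difference (points) | Chance, 80 per arm | Chance, 56 per arm |
|---|---|---|---|---|
| no selection | – | −15.0 | 5.3% | 5.0% |
| 25% lower | 30% | −13.9 | 8.1% | 7.1% |
| 25% lower | 50% | −13.1 | 10.6% | 8.9% |
| 25% lower | 70% | −12.4 | 13.7% | 11.1% |
| 50% lower | 30% | −12.75 | 12.0% | 9.9% |
| 50% lower | 50% | −11.25 | 19.8% | 15.5% |
| 50% lower | 70% | −9.75 | 31.3% | 23.6% |

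**Sensitivity of the result, 80 per arm.**

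- *Eye chosen without regard to severity*, milder-eye failure halved, 30/50/70% bilateral: 8.1/10.6/13.7%.
- *Same absolute difference in milder eyes*: the analysed difference stays at −15 points and the chance stays at 5.3%.
- *A different model*, with remission odds doubled in milder eyes, 50% bilateral and an unpooled Wald limit: the difference shrinks to −11.8 points, and the chance rises from 6.1% with no selection to 18.9%.
- *Worse eyes taken*, with remission odds halved, 50% bilateral and the same Wald limit: the difference widens to −19.2 points and the chance falls to 1.1%.

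**The case against.** The strongest reply is that the percentages above are not type I error for the comparison as the protocol defines it. The protocol compares one investigator-selected eye per subject and does not tie the 15-point margin to worse eyes. If the analysed eyes truly differ by 9.75 to 13.9 points, the product is inside the margin in those eyes, and passing is power. When the analysed eyes themselves are set at −15 points (control 94.9–96.1%, same interval, 80 per arm), the chance stays at 5.3%. This stands. What is left is a question about which eyes the conclusion describes, and about assay sensitivity.

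The direction is also not settled. No section says that milder eyes are, or tend to be, chosen, and an investigator may equally take the eye that brought the patient in. Dilution further needs a smaller absolute difference in milder eyes, which is an assumption. In addition, section 8.3.1 plans a chi-square or Fisher test and describes no non-inferiority interval, so the decision rule used above is itself assumed.

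Two stronger readings are tempting. A reader might infer that free choice of eye biases the comparison between arms. The documents do not support that: selection precedes assignment in the listed order, the investigator is blinded, and balance within centres keeps differing site habits from loading onto one arm. A reader might also infer that bilateral disease is frequent and that both eyes are already graded. Section 5.1.2 says only that symptoms can become bilateral, with no frequency. Sections 6.4.3.1 and 6.4.4 do not say that hyperemia and secretion are graded in both eyes; only swabbing of both eyes is explicit.

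The reply does not remove the gap. How severe the analysed eyes are, and so how easily a difference can be seen, is left to unstated site practice.

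**Conclusion.** The concern holds as a possible loss of assay sensitivity; neither differential bias nor a demonstrated inflation of type I error follows from the documents. The analysed eye is chosen without a criterion, and nothing requires it to show the inclusion signs. If milder eyes are taken, and if the absolute treatment difference is smaller in them, the observed difference moves toward non-inferiority.

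The size cannot be derived from the documents. The range of 8–31% against about 5%, at 80 per arm, depends on the product being at the margin in worse eyes, 30–70% bilateral cases, failure 25–50% lower in milder eyes, and the milder eye always being chosen. It is an illustration, not an estimate. The point should be corrected because the rule is cheap to set now and eye selection cannot be redone later.

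**What to change.** Replace the selection sentence in section 6.5.2.1 with a fixed rule along these lines:

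*The study eye must itself meet the inclusion signs. If both eyes do, the study eye is the one with the higher baseline sum of hyperemia grade and secretion grade; if tied, the eye with the higher secretion grade; if still tied, the right eye. Baseline grades for both eyes and the selected eye are recorded in the CRF before treatment assignment.*

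The sum serves only to rank the two eyes and creates no new endpoint. Another rule fixed in advance, such as first-affected eye or random choice, would also remove the investigator's discretion. The worse-eye rule is preferred because it keeps the analysis in the eyes where a difference is most likely to show.

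The cost is one protocol sentence, one added CRF entry for the fellow eye and a check on its timing. Observed remission may be slightly lower in both arms. No treatment, visit or sample size changes.
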